Enrolled participants were randomly divided into probiotics group or placebo group. Seventeen and 19 participants were respectively assigned to the placebo group and the probiotics group. The probiotics we used were in the form of 100mg L. bulgaricus powder packets, each containing 1×10^8 CFU of probiotics (TCI CO., Taipei, Taiwan). Initially (day 1), participants underwent measurements for weight, body fat, and BMI, and fasting blood

[figure not shown]
IRB/REC No. :	CMUH110-REC2-070
Page No. :	5/28

samples were collected. Subsequently, each participant received one package of either probiotic or a placebo sample, along with drinking water on the same day. From that point onward, participants self-administered one package of the sample daily for 12 weeks and the participants' sample consumption and physical conditions were tracked by the research assistants weekly. Throughout the study duration, participants maintained their regular diet and lifestyle. At the endpoint (day 84), weight, body fat, and BMI were measured, and fasting blood samples were collected again. Weight and body fat were measured with Karada Scan 216 (OMRON, Kyoto, Japan). Alanine aminotransferase (ALT), aspartate aminotransferase (AST), blood urea nitrogen (BUN), creatinine (CRE), CHOL, HDL-C, LDL-C, TG, hemoglobin A1c (HbA1c), and Glucose-Ante Cibum (Glu-AC) levels were analyzed and reported by Laboratory Medicine in Chinese Medical University Hospital (Taichung, Taiwan). Data were expressed as the mean \pm standard error of the mean (SEM). Statistical significance between groups were done by student paired t-test or Mann-Whitney test. P-values lower than 0.05 were considered statistically significant.

Data Analysis:

The statistical analysis was conducted using GraphPad's unpaired independent samples t-test, with significance set at $*P < 0.05$.

Flow Diagram of the study:

Group	Placebo		Probiotics	
	Mean	SD	Mean	SD
Age, years	41.38	12.71	41.56	10.92
Gender, male/female	7/6		12/6	
Weight, kg	78.69	15.64	80.77	15.11
Body fat, %	32.08	6.65	30.84	5.26
BMI	29.32	5.40	28.89	3.59
ALT, U/L	26.00	15.37	32.63	18.96
AST, U/L	21.45	10.62	23.36	7.44
BUN, mg/dL	13.10	2.69	13.67	2.94
CRE, mg/dL	0.80	0.14	0.83	0.15
CHOL, mg/dL	182.18	43.04	201.60	40.97
HDL-C, mg/dL	46.82	5.82	48.50	16.26
LDL-C, mg/dL	122.82	42.15	111.01	30.40
TG, mg/dL	139.62	52.18	220.94	173.92
HbA1c, %	5.80	0.83	6.17	1.07
Glu-AC, mg/dL	93.45	16.92	109.06	34.13

Table 1: Analysis of Baseline Values of the Participants

Results

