Placebo represents the placebo control group, and Probiotics represents the probiotics experimental group. Individual comparisons of changes in lipids carried by serum lipoproteins before and after sample consumption are depicted. The size of the points in the scatter plot ($-\log_{10}$ p values) and the color (log2 fold change denoted as log2FC, with red indicating positive correlation changes and blue indicating negative correlation changes) are used to distinguish between inter-group differences and trends. Serum very low-density lipoprotein (VLDL), low-density lipoprotein (LDL), and high-density lipoprotein (HDL) have the ability to carry cholesterol (Chol), lipids, cholesterol esters (CE), and triglycerides (TG) individually. The experimental data indicate that probiotics upregulate the content of

IRB/REC No. :	CMUH110-REC2-070
Page No. :	13/28

lipids carried by HDL (Chol:Lipid and CE:Lipid). Simultaneously, there is a significant decrease in the total amount of lipids carried by VLDL (L-VLDL, XL-VLDL, XXL-VLDL). Additionally, there is a significant decrease in triglycerides (TG) carried by both VLDL and HDL.

IRB/REC No. :	CMUH110-REC2-070
Page No. :	14/28

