L-HDL-FC %	Free cholesterol to total lipids ratio in large HDL	%
L-HDL-TG %	Triglycerides to total lipids ratio in large HDL	%
M-HDL-PL %	Phospholipids to total lipids ratio in medium HDL	%
M-HDL-C %	Cholesterol to total lipids ratio in medium HDL	%
M-HDL-CE %	Cholesteryl esters to total lipids ratio in medium HDL	%
M-HDL-FC %	Free cholesterol to total lipids ratio in medium HDL	%
M-HDL-TG %	Triglycerides to total lipids ratio in medium HDL	%
S-HDL-PL %	Phospholipids to total lipids ratio in small HDL	%
S-HDL-C %	Cholesterol to total lipids ratio in small HDL	%
S-HDL-CE %	Cholesteryl esters to total lipids ratio in small HDL	%
S-HDL-FC %	Free cholesterol to total lipids ratio in small HDL	%
S-HDL-TG %	Triglycerides to total lipids ratio in small HDL	%

IRB/REC No. :	CMUH110-REC2-070
Page No. :	20/28

Table 4: Comparative Analysis of Metabolomic Pre-test and Post-test Results for Placebo Group Blood Samples

Differential expression analysis								
Significance(p-value)	Feature	Mean(after)	Mean(before)	Method	FC	Log2(FC)	-Log10(p-value)	-Log10(padj)
yes	Creatinine	64.21	59.285	t-test	0.923	-0.115	2.023	0.103
yes	IDL_CE_pct	51.149	49.621	t-test	0.97	-0.044	2.623	0.527
yes	IDL_C_pct	67.73	66.121	t-test	0.976	-0.035	2.767	0.527
yes	IDL_TG_pct	8.787	10.075	t-test	1.147	0.197	1.332	0.06
yes	L_LDL_CE_pct	53.99	53.463	t-test	0.99	-0.014	1.562	0.06
yes	L_LDL_C_pct	71.967	71.136	t-test	0.988	-0.017	1.59	0.06
yes	L_LDL_TG_pct	5.966	6.83	t-test	1.145	0.195	1.397	0.06
yes	M_LDL_PL_pct	26.658	26.309	t-test	0.987	-0.019	1.452	0.06
no	Acetate	0.017	0.019	t-test	1.092	0.126	0.309	0.06
no	Acetoacetate	0.025	0.019	t-test	0.741	-0.432	0.366	0.06
no	Acetone	0.019	0.021	t-test	1.063	0.089	0.067	0.005
no	Ala	0.337	0.383	t-test	1.137	0.185	1.234	0.06
no	Albumin	41.434	40.602	t-test	0.98	-0.029	0.259	0.06
no	ApoA1	1.416	1.353	t-test	0.955	-0.066	0.477	0.06
no	ApoB	0.878	0.858	t-test	0.977	-0.033	0.24	0.06
no	ApoB_by_ApoA1	0.63	0.642	t-test	1.019	0.027	0.179	0.027
no	bOHbutyrate	0.094	0.103	t-test	1.1	0.137	0.063	0.005
no	Cholines	2.554	2.454	t-test	0.961	-0.058	0.361	0.06
no	Citrate	0.06	0.063	t-test	1.043	0.061	1.126	0.06
no	Clinical_LDL_C	2.787	2.6	t-test	0.933	-0.101	0.605	0.06
no	DHA	0.323	0.291	t-test	0.9	-0.152	0.271	0.06
no	DHA_pct	2.574	2.387	t-test	0.927	-0.109	0.292	0.06
no	Gln	0.487	0.495	t-test	1.016	0.022	0.099	0.005
no	Glucose	4.525	3.994	t-test	0.883	-0.18	0.749	0.06
no	Gly	0.251	0.302	t-test	1.202	0.265	1.129	0.06
no	GlycA	0.857	0.83	t-test	0.968	-0.046	0.294	0.06

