no	XXL_VLDL_P	0	0	t-test	0.992	-0.012	0.01	0.002
no	XXL_VLDL_PL	0.026	0.026	t-test	0.986	-0.021	0.017	0.002
no	XXL_VLDL_PL_pct	14.889	16.636	t-test	1.117	0.16	0.527	0.06
no	XXL_VLDL_TG	0.084	0.074	t-test	0.879	-0.187	0.136	0.01
no	XXL_VLDL_TG_pct	34.697	43.814	t-test	1.263	0.337	0.413	0.06

IRB/REC No. :	CMUH110-REC2-070
Page No. :	25/28

Table 5: Comparative Analysis of Metabolomic Pre-test and Post-test Results for Probiotics Group Blood Samples

Differential expression analysis								
Significance(p-value)	Feature	Mean(after)	Mean(before)	Method	FC	Log2(FC)	-Log10(p-value)	-Log10(padj)
yes	Acetate	0.017	0.019	t-test	1.156	0.209	1.329	0.407
yes	Gly	0.263	0.295	t-test	1.123	0.167	1.447	0.407
yes	HDL_size	9.573	9.508	t-test	0.993	-0.01	1.433	0.407
yes	Lactate	4.175	5.984	t-test	1.433	0.519	1.441	0.407
yes	L_VLDL_CE_pct	14.036	15.354	t-test	1.094	0.129	1.363	0.407
yes	L_VLDL_C_pct	28.119	29.999	t-test	1.067	0.093	1.505	0.407
yes	L_VLDL_FC_pct	14.083	14.645	t-test	1.04	0.056	1.643	0.421
yes	L_VLDL_L	0.563	0.48	t-test	0.853	-0.229	1.334	0.407
yes	L_VLDL_TG	0.288	0.233	t-test	0.81	-0.304	2.037	0.533
yes	L_VLDL_TG_pct	51.128	49.056	t-test	0.959	-0.06	1.429	0.407
yes	M_HDL_CE_pct	37.7	39.269	t-test	1.042	0.059	2.902	0.805
yes	M_HDL_C_pct	46.11	47.515	t-test	1.03	0.043	3.121	0.805
yes	M_HDL_PL_pct	47.018	46.34	t-test	0.986	-0.021	1.977	0.533
yes	M_HDL_TG_pct	6.873	6.145	t-test	0.894	-0.161	1.715	0.463
yes	M_VLDL_PL_pct	21.414	22.043	t-test	1.029	0.042	1.319	0.407
yes	S_HDL_CE_pct	27.533	28.901	t-test	1.05	0.07	1.987	0.533
yes	S_HDL_C_pct	37.973	39.337	t-test	1.036	0.051	2.162	0.533
yes	S_HDL_PL_pct	55.964	55.036	t-test	0.983	-0.024	1.839	0.52
yes	S_HDL_TG_pct	6.063	5.628	t-test	0.928	-0.107	1.571	0.407
yes	S_LDL_C_pct	62.862	63.718	t-test	1.014	0.019	2.566	0.645
yes	TG_by_PG	0.778	0.696	t-test	0.895	-0.161	1.792	0.508
yes	VLDL_size	39.666	39.173	t-test	0.988	-0.018	2.006	0.533
yes	VLDL_TG	1.623	1.384	t-test	0.853	-0.229	1.355	0.407
yes	XL_HDL_CE_pct	36.249	38.447	t-test	1.061	0.085	1.922	0.524
yes	XL_HDL_C_pct	52.182	56.422	t-test	1.081	0.113	1.345	0.407
yes	XL_VLDL_L	0.381	0.323	t-test	0.847	-0.239	1.334	0.407
yes	XL_VLDL_TG	0.221	0.181	t-test	0.818	-0.291	1.843	0.52
yes	XXL_VLDL_L	0.467	0.375	t-test	0.804	-0.315	1.494	0.407
yes	XXL_VLDL_P	0	0	t-test	0.817	-0.292	1.395	0.407
yes	XXL_VLDL_TG	0.267	0.202	t-test	0.756	-0.403	2.073	0.533
no	Acetoacetate	0.026	0.017	t-test	0.651	-0.619	0.697	0.243
no	Acetone	0.016	0.02	t-test	1.238	0.308	0.6	0.219

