no	S_HDL_PL	0.727	0.72	t-test	0.991	-0.013	0.079	0.026
no	S_HDL_TG	0.082	0.08	t-test	0.967	-0.049	0.238	0.1
no	S_LDL_C	0.225	0.232	t-test	1.035	0.05	0.388	0.158
no	S_LDL_CE	0.173	0.178	t-test	1.026	0.037	0.24	0.1
no	S_LDL_CE_pct	48.121	48.302	t-test	1.004	0.005	0.188	0.073
no	S_LDL_FC	0.051	0.055	t-test	1.067	0.093	1.031	0.384
no	S_LDL_FC_pct	14.741	15.416	t-test	1.046	0.065	0.854	0.308
no	S_LDL_L	0.358	0.365	t-test	1.021	0.029	0.212	0.081
no	S_LDL_P	0	0	t-test	1.021	0.03	0.194	0.074
no	S_LDL_PL	0.106	0.107	t-test	1.009	0.012	0.089	0.027
no	S_LDL_PL_pct	29.648	29.377	t-test	0.991	-0.013	0.371	0.158
no	S_LDL_TG	0.028	0.026	t-test	0.948	-0.076	0.358	0.158
no	S_LDL_TG_pct	7.49	6.906	t-test	0.922	-0.117	0.774	0.274
no	Sphingomyelins	0.477	0.472	t-test	0.989	-0.015	0.088	0.027
no	S_VLDL_C	0.199	0.206	t-test	1.033	0.047	0.162	0.057
no	S_VLDL_CE	0.126	0.131	t-test	1.04	0.056	0.193	0.074
no	S_VLDL_CE_pct	21.368	22.914	t-test	1.072	0.101	1.147	0.407
no	S_VLDL_C_pct	33.978	36.404	t-test	1.071	0.1	1.189	0.407
no	S_VLDL_FC	0.073	0.074	t-test	1.022	0.031	0.105	0.03
no	S_VLDL_FC_pct	12.61	13.49	t-test	1.07	0.097	1.238	0.407
no	S_VLDL_L	0.61	0.595	t-test	0.975	-0.037	0.123	0.039

IRB/REC No. :	CMUH110-REC2-070
Page No. :	28/28

no	S_VLDL_P	0	0	t-test	0.966	-0.05	0.165	0.057
no	S_VLDL_PL	0.133	0.133	t-test	0.998	-0.003	0.008	0.004
no	S_VLDL_PL_pct	22.398	23.208	t-test	1.036	0.051	1.163	0.407
no	S_VLDL_TG	0.279	0.257	t-test	0.922	-0.117	0.453	0.179
no	S_VLDL_TG_pct	43.624	40.388	t-test	0.926	-0.111	1.19	0.407
no	Total_BCAA	0.486	0.521	t-test	1.071	0.099	0.842	0.308
no	Total_C	5.128	5.17	t-test	1.008	0.012	0.07	0.024
no	Total_CE	3.693	3.734	t-test	1.011	0.016	0.1	0.028
no	Total_FA	16.38	15.438	t-test	0.943	-0.085	0.618	0.22
no	Total_FC	1.435	1.436	t-test	1.001	0.001	0.005	0.003
no	Total_L	10.668	10.37	t-test	0.972	-0.041	0.248	0.103
no	Total_P	0.018	0.018	t-test	0.999	-0.001	0.008	0.004
no	Total_PL	3.313	3.224	t-test	0.973	-0.039	0.239	0.1
no	Total_TG	2.227	1.976	t-test	0.887	-0.172	1.011	0.384
no	Tyr	0.066	0.07	t-test	1.046	0.065	0.448	0.177
no	Unsaturation	1.369	1.37	t-test	1	0.001	0.018	0.004
no	Val	0.272	0.288	t-test	1.06	0.084	0.657	0.227
no	VLDL_C	0.929	0.909	t-test	0.978	-0.031	0.107	0.03
no	VLDL_CE	0.523	0.526	t-test	1.004	0.006	0.02	0.004
no	VLDL_FC	0.406	0.383	t-test	0.945	-0.082	0.314	0.139
no	VLDL_L	3.254	2.949	t-test	0.906	-0.142	0.708	0.245
no	VLDL_P	0	0	t-test	0.958	-0.063	0.261	0.111
no	VLDL_PL	0.702	0.655	t-test	0.934	-0.099	0.411	0.159

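### The Figure 5 legend reports algebraically linked Table 5 rows as separate significant lipid results, and its HDL triglyceride statement has no concentration row behind it

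*Combined protocol and SAP*

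**What the plan says.** Methods and Design sets the threshold: "P-values lower than 0.05 were considered statistically significant". Tables 4 and 5 in the Appendix carry the column headings "Significance(p-value) Feature Mean(after) Mean(before) Method FC Log2(FC) -Log10(p-value) -Log10(padj", so the yes/no flag rests on the raw p-value and the adjusted value stands in a separate column.

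Table 3 defines each share as a ratio within one particle, for example "Cholesterol to total lipids ratio in medium HDL". Table 5 (probiotics arm, pre-test against post-test) flags several shares of the same particle, including "yes M_HDL_C_pct 46.11 47.515 t-test 1.03 0.043 3.121 0.805" and "yes M_HDL_TG_pct 6.873 6.145 t-test 0.894 -0.161 1.715 0.463".

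The Figure 5 legend in Results makes four statements. Probiotics raise the lipid content of HDL, shown as the cholesterol and cholesteryl ester ratios to lipid. For VLDL, "there is a significant decrease in the total amount of lipids carried by VLDL (L-VLDL, XL-VLDL, XXL-VLDL". Triglyceride falls significantly in VLDL. Triglyceride also falls significantly in HDL.

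The same table holds the whole-class rows "no VLDL_L 3.254 2.949 t-test 0.906 -0.142 0.708 0.245" and "no Total_TG 2.227 1.976 t-test 0.887 -0.172 1.011 0.384". The documents nowhere say that these rows are linked.

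**The concern.** Four statements in a row read as four pieces of agreeing evidence. If some are fixed by arithmetic once others are known, the agreement is partly built in. A share can also fall without any fall in the amount of that lipid, so a flagged triglyceride share is not evidence that HDL carries less triglyceride.

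This matters because the legends of Figures 1 to 4 report no significant difference between groups in body composition, glucose indices, blood lipids, or liver and kidney function. Figure 5 is where the favourable lipid claim is made, so its wording largely decides what a reader takes from the trial.

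**Working it through.** **Inputs.** All rows are from Table 5, with p = 10^-(printed -log10 p).

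**1. The printed adjusted value.** Table 5 has 250 rows. M_HDL_CE_pct has p = 10^-2.902 = 0.00125, and 0.00125 × 250/2 = 0.157. M_HDL_C_pct has p = 10^-3.121 = 0.00076, and 0.00076 × 250/1 = 0.189; Benjamini-Hochberg takes the smaller, 0.157. The printed value is 10^-0.805 = 0.157, so it is reproduced. It is the smallest in the table.

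**2. Sign convention.** The printed fold change is the second mean over the first: 47.515/46.11 = 1.03. The legend's directions also need second minus first. The headings call the first column after and the second before, which gives the opposite directions. I use second minus first below. Table 2 agrees for triglyceride (-21.00, against Total_TG 2.227 to 1.976) but not for creatinine (+0.0475, against 72.354 to 68.671). The headings therefore need checking against the data. The p-values do not depend on this.

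**3. HDL shares.**

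| Particle | C% | PL% | TG% | Sum of changes |
|---|---|---|---|---|
| Medium HDL | 46.110 to 47.515 (+1.405) | 47.018 to 46.340 (-0.678) | 6.873 to 6.145 (-0.728) | -0.001 |
| Small HDL | 37.973 to 39.337 (+1.364) | 55.964 to 55.036 (-0.928) | 6.063 to 5.628 (-0.435) | +0.001 |

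The levels sum to 100 within rounding, for example 46.110 + 47.018 + 6.873 = 100.001. Cholesteryl ester is part of cholesterol: in medium HDL, CE% + FC% = 37.700 + 8.409 = 46.109, against C% 46.110. In each particle four of the five shares are flagged, although only three can vary freely.

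**4. HDL amounts.** None of the concentration rows behind the two HDL statements is flagged:
- HDL_TG: 10^-0.361 = 0.436. By subclass: XL 0.421, L 0.438, M 0.374, S 0.578.
- HDL_L: 10^-0.286 = 0.52. HDL_C: 10^-0.151 = 0.71.

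**5. VLDL, whole and part.**

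| Particle | Change in total lipids (p) | Change in TG (p) | TG/total |
|---|---|---|---|
| L-VLDL | 0.480 - 0.563 = -0.083 (0.046) | 0.233 - 0.288 = -0.055 (0.009) | 0.66 |
| XL-VLDL | 0.323 - 0.381 = -0.058 (0.046) | 0.181 - 0.221 = -0.040 (0.014) | 0.69 |
| XXL-VLDL | 0.375 - 0.467 = -0.092 (0.032) | 0.202 - 0.267 = -0.065 (0.009) | 0.71 |

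No cholesterol, cholesteryl ester, free cholesterol or phospholipid concentration in these three particles is flagged.

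**6. VLDL class rows.** The six subclasses add up to VLDL_L: 0.467 + 0.381 + 0.563 + 0.816 + 0.610 + 0.417 = 3.254, and 2.949 for the second column.
- VLDL_L: p = 10^-0.708 = 0.196.
- Total_TG: p = 10^-1.011 = 0.097.
- VLDL_TG: p = 10^-1.355 = 0.044, adjusted 10^-0.407 = 0.39.
- VLDL_size: p = 10^-2.006 = 0.0099, adjusted 10^-0.533 = 0.29.

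**7. Extent.** Of the 30 flags in Table 5, 16 are shares, and 14 of those lie in four particles (M_HDL 4, S_HDL 4, L_VLDL 4, XL_HDL 2).

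**The case against.** The best defence is that the tables are open about all this. They print the class rows and the adjusted values, and the VLDL statement names the three subclasses, each with raw p below 0.05. The flagged VLDL_size row fits a change confined to large particles, which a class total could hide. This stands: a reader might infer that VLDL_L contradicts the legend, but it only limits how far the statement reaches. It also means that testing class totals first is a debatable choice, not a requirement.

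A reader might also infer that everything collapses to a single shift. It does not. Five shares have three free dimensions, and phospholipid supplies 0.678/1.405 = 48% of the medium HDL cholesterol change and 0.928/1.364 = 68% of the small HDL change. A cholesterol-to-triglyceride log-ratio would discard that part. Nor is the 100% sum universal in print: three columns fall short (Table 4 XL_HDL second and XXL_VLDL first, 85.7; Table 5 XXL_VLDL second, 88.9). No flagged row is affected.

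Finally, a reader might infer that the linked rows spoil the adjusted values or cost power, so that a smaller family would rescue the HDL result. The documents do not support this. Benjamini-Hochberg over the 14 particles gives a minimum of 0.011 with the cholesterol shares, but 0.101 with phospholipid and 0.151 with triglyceride. The answer depends on a choice made after seeing the data, and all of these are within-arm values.

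Figure 5 itself is not shown, so the point rests on its legend and on Tables 3 and 5.

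**Conclusion.** The concern holds for the legend's wording. The HDL ratio rise and the HDL triglyceride fall overlap as views of one change in composition in medium and small HDL. The claims of lower triglyceride carried by HDL and higher HDL lipid content have no concentration row behind them (p = 0.436, 0.52 and 0.71). The VLDL total-lipid and triglyceride statements are whole and part, with triglyceride 66-71% of the change. The VLDL triglyceride statement has a class row behind it on raw p only (0.044); VLDL_L (0.196) and Total_TG (0.097) are not significant. No row in Table 5 reaches an adjusted p below 0.05.

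The printed adjusted values are not shown to be wrong. The fault lies in reading linked, raw, within-arm results as separate findings. The directions assume second column minus first, as the legend and the fold changes do.

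**What to change.** Rewrite the Figure 5 legend:

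1. Merge the HDL statements into one composition (share) result for the named subclasses. Remove the claim of a significant fall in triglyceride carried by HDL, and quote HDL_TG p = 0.436.
2. Limit the VLDL statement to L-, XL- and XXL-VLDL at raw p, and say that triglyceride is the larger part of that change. Quote VLDL_L p = 0.196, Total_TG p = 0.097, VLDL_TG p = 0.044 and VLDL_size p = 0.0099 beside it.
3. State that no row passes on the printed adjusted p-value and that Table 5 is a within-arm comparison. Support any treatment claim with the probiotic-minus-placebo difference in change, labelled exploratory.
4. Reconcile the after and before headings of Tables 4 and 5 with the fold changes, the legend and Table 2.

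The cost is a text edit and a small re-run on data in hand. The downside is a less favourable legend.

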Appendix

Figure 5: Extracted Meaningful Components from Metabolomic Analysis Results, Other Results Provided in the Appendix °

Table 3: List of Name Abbreviations and Units

Excel column name	Biomarker name	Unit
Total-C	Total cholesterol	mmol/l
non-HDL-C	Total cholesterol minus HDL-C	mmol/l
Remnant-C	Remnant cholesterol (non-HDL, non-LDL -cholesterol)	mmol/l
VLDL-C	VLDL cholesterol	mmol/l
Clinical LDL-C	Clinical LDL cholesterol	mmol/l
LDL-C	LDL cholesterol	mmol/l
HDL-C	HDL cholesterol	mmol/l
Total-TG	Total triglycerides	mmol/l
VLDL-TG	Triglycerides in VLDL	mmol/l
LDL-TG	Triglycerides in LDL	mmol/l
HDL-TG	Triglycerides in HDL	mmol/l
Total-PL	Total phospholipids in lipoprotein particles	mmol/l
VLDL-PL	Phospholipids in VLDL	mmol/l
LDL-PL	Phospholipids in LDL	mmol/l
HDL-PL	Phospholipids in HDL	mmol/l
Total-CE	Total esterified cholesterol	mmol/l
VLDL-CE	Cholesteryl esters in VLDL	mmol/l
LDL-CE	Cholesteryl esters in LDL	mmol/l
HDL-CE	Cholesteryl esters in HDL	mmol/l
Total-FC	Total free cholesterol	mmol/l
VLDL-FC	Free cholesterol in VLDL	mmol/l
LDL-FC	Free cholesterol in LDL	mmol/l
HDL-FC	Free cholesterol in HDL	mmol/l
Total-L	Total lipids in lipoprotein particles	mmol/l
VLDL-L	Total lipids in VLDL	mmol/l
LDL-L	Total lipids in LDL	mmol/l
HDL-L	Total lipids in HDL	mmol/l
Total-P	Total concentration of lipoprotein particles	mmol/l
VLDL-P	Concentration of VLDL particles	mmol/l
LDL-P	Concentration of LDL particles	mmol/l
HDL-P	Concentration of HDL particles	mmol/l
VLDL size	Average diameter for VLDL particles	nm
LDL size	Average diameter for LDL particles	nm
HDL size	Average diameter for HDL particles	nm
Phosphoglyc	Phosphoglycerides	mmol/l

IRB/REC No. :	CMUH110-REC2-070
Page No. :	15/28

TG/PG	Ratio of triglycerides to phosphoglycerides	ratio
Cholines	Total cholines	mmol/l
Phosphatidylc	Phosphatidylcholines	mmol/l
Sphingomyelins	Sphingomyelins	mmol/l
ApoB	Apolipoprotein B	g/l
ApoA1	Apolipoprotein A1	g/l
ApoB/ApoA1	Ratio of apolipoprotein B to apolipoprotein A1	ratio
Total-FA	Total fatty acids	mmol/l
Unsaturation	Degree of unsaturation	degree
Omega-3	Omega-3 fatty acids	mmol/l
Omega-6	Omega-6 fatty acids	mmol/l
PUFA	Polyunsaturated fatty acids	mmol/l
MUFA	Monounsaturated fatty acids	mmol/l
SFA	Saturated fatty acids	mmol/l
LA	Linoleic acid	mmol/l
DHA	Docosahexaenoic acid	mmol/l
Omega-3 %	Ratio of omega-3 fatty acids to total fatty acids	%
Omega-6 %	Ratio of omega-6 fatty acids to total fatty acids	%

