no	Ala	0.373	0.401	t-test	1.074	0.103	0.738	0.264
no	Albumin	41.766	43.735	t-test	1.047	0.066	1.025	0.384
no	ApoA1	1.521	1.487	t-test	0.978	-0.032	0.18	0.068
no	ApoB	1.001	1.016	t-test	1.015	0.021	0.123	0.039
no	ApoB_by_ApoA1	0.669	0.698	t-test	1.044	0.062	0.667	0.227
no	boHbutyrate	0.074	0.09	t-test	1.218	0.284	0.375	0.158
no	Cholines	2.989	2.88	t-test	0.963	-0.054	0.368	0.158
no	Citrate	0.062	0.062	t-test	1.012	0.017	0.143	0.052
no	Clinical_LDL_C	2.854	3	t-test	1.051	0.072	0.548	0.211
no	Creatinine	72.354	68.671	t-test	0.949	-0.075	0.784	0.275
no	DHA	0.287	0.269	t-test	0.94	-0.09	0.163	0.057
no	DHA_pct	1.763	1.862	t-test	1.056	0.079	0.258	0.111
no	Gln	0.546	0.549	t-test	1.006	0.009	0.072	0.024
no	Glucose	4.989	4.441	t-test	0.89	-0.168	0.66	0.227
no	GlycA	0.94	0.938	t-test	0.998	-0.003	0.029	0.004
no	Glycerol	0.099	0.119	t-test	1.202	0.265	0.326	0.144
no	HDL_C	1.29	1.262	t-test	0.978	-0.032	0.151	0.054
no	HDL_CE	0.986	0.971	t-test	0.985	-0.022	0.103	0.029
no	HDL_FC	0.303	0.291	t-test	0.957	-0.063	0.324	0.144
no	HDL_L	3.102	2.984	t-test	0.962	-0.056	0.286	0.122
no	HDL_P	0.016	0.016	t-test	0.997	-0.004	0.021	0.004
no	HDL_PL	1.592	1.515	t-test	0.952	-0.071	0.39	0.158
no	HDL_TG	0.22	0.208	t-test	0.942	-0.085	0.361	0.158

IRB/REC No. :	CMUH110-REC2 -070
Page No. :	26/28

no	His	0.075	0.083 t-test	1.115	0.157	0.962	0.364
no	IDL_C	0.867	0.864 t-test	0.997	-0.004	0.022	0.004
no	IDL_CE	0.654	0.648 t-test	0.991	-0.013	0.086	0.027
no	IDL_CE_pct	49.557	49.108 t-test	0.991	-0.013	0.588	0.219
no	IDL_C_pct	65.567	65.379 t-test	0.997	-0.004	0.198	0.074
no	IDL_FC	0.212	0.216 t-test	1.018	0.025	0.156	0.057
no	IDL_FC_pct	16.01	16.271 t-test	1.016	0.023	0.405	0.158
no	IDL_L	1.321	1.326 t-test	1.004	0.006	0.036	0.004
no	IDL_P	0	0 t-test	0.96	-0.059	0.352	0.158
no	IDL_PL	0.305	0.313 t-test	1.026	0.036	0.298	0.127
no	IDL_PL_pct	23.096	23.591 t-test	1.021	0.031	0.914	0.337
no	IDL_TG	0.149	0.149 t-test	0.998	-0.003	0.013	0.004
no	IDL_TG_pct	11.338	11.03 t-test	0.973	-0.04	0.297	0.127
no	Ile	0.072	0.076 t-test	1.053	0.074	0.458	0.179
no	LA	5.312	5.015 t-test	0.944	-0.083	0.6	0.219
no	LA_pct	33.147	34.014 t-test	1.026	0.037	0.435	0.172
no	LDL_C	2.043	2.135 t-test	1.045	0.064	0.627	0.222
no	LDL_CE	1.542	1.603 t-test	1.039	0.055	0.518	0.189
no	LDL_FC	0.5	0.532 t-test	1.064	0.09	0.967	0.364
no	LDL_L	2.992	3.111 t-test	1.04	0.056	0.496	0.184
no	LDL_P	0.001	0.001 t-test	1.035	0.05	0.367	0.158
no	LDL_PL	0.714	0.741 t-test	1.037	0.052	0.43	0.172

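### The Figure 5 text gives no LDL result and calls within-arm changes significant; against placebo, no VLDL triglyceride, HDL triglyceride or LDL cholesterol difference is established, and VLDL triglycerides and LDL cholesterol move in opposite directions

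*Combined protocol and SAP*

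**What the plan says.** The Figure 5 legend (Results) introduces VLDL, LDL and HDL as lipid carriers and says the display separates inter-group differences and trends. It then states three findings: cholesterol and cholesteryl ester as a share of HDL lipid went up, total lipid in the L, XL and XXL VLDL classes went down significantly, and "there is a significant decrease in triglycerides (TG) carried by both VLDL and HDL". It states no LDL finding. The Appendix describes the figure as "Extracted Meaningful Components from Metabolomic Analysis Results, Other Results Provided in the Appendix".

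The data are in Appendix Table 4 (placebo) and Table 5 (probiotics). Each compares before with after inside one arm; neither compares arms. Clinical LDL cholesterol reads "no Clinical_LDL_C 2.854 3 t-test 1.051 0.072 0.548 0.211" on probiotics and "no Clinical_LDL_C 2.787 2.6 t-test 0.933 -0.101 0.605 0.06" on placebo. The columns run: flag, feature, Mean(after), Mean(before), method, FC (fold change), log2 FC, -log10 p, -log10 adjusted p. One LDL composition row is flagged significant on probiotics but is not mentioned in the legend: "yes S_LDL_C_pct 62.862 63.718 t-test 1.014 0.019 2.566 0.645".

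**The concern.** Blood lipids are part of the stated primary goal, and LDL-C above 130 mg/dL is one of the protocol's own risk criteria. A reader of the Figure 5 text meets only changes described as significant, in two of the three carriers. In a randomised comparison the relevant quantity is the difference in change between arms. A change that passes 0.05 in one arm and not in the other does not show that the arms differ. If VLDL triglycerides and LDL cholesterol move in opposite directions relative to placebo, with similar uncertainty, describing one as a significant decrease and leaving the other out gives an unbalanced lipid conclusion.

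The HDL triglyceride statement has a further problem: the rows that measure the amount of triglyceride in HDL are flagged as not significant.

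**Working it through.** **Reproducing the printed fold change.** Second mean over first: 3/2.854 = 1.051 and 2.6/2.787 = 0.933, both as printed. The inverse, 2.854/3 = 0.951, does not match. So FC treats the second column as the later one, while the headings call it the earlier one. The FC reading agrees with the legend (VLDL down on probiotics) and with Table 2 for LDL-C and TG in both arms. It does not agree everywhere: creatinine on probiotics rises by 0.0475 mg/dL in Table 2 but has FC 0.949 in Table 5. The FC direction is used below, subject to confirmation.

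**LDL rows.** Each table has 29 LDL amount or particle rows: Clinical_LDL_C plus seven each for total, large, medium and small LDL. Without the four triglyceride rows, 25 remain.
- Probiotics: 25 of 25 have FC above 1; raw p from 10^-1.039 = 0.091 to 0.81.
- Placebo: 25 of 25 have FC below 1; raw p from 0.217 to 0.64.
- The LDL triglyceride rows do not fit (placebo; probiotics): total 1.097; 1.002, large 1.103; 1.015, medium 1.094; 0.995, small 1.063; 0.948.

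Table 2 LDL-C changes are +6.012 (SEM 4.366) on probiotics and -12.04 (SEM 6.323) mg/dL on placebo, the same direction.

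**HDL triglycerides in Table 5.** HDL_TG has p = 10^-0.361 = 0.44. The XL, L, M and S amounts have p = 0.42, 0.44, 0.37 and 0.58. All are flagged 'no'. Only the percentages M_HDL_TG_pct (p = 0.019) and S_HDL_TG_pct (p = 0.027) are flagged.

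**Adjustment.** The smallest adjusted p in Table 5 is 10^-0.805 = 0.157, so no row passes 0.05 after adjustment.

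**Between-arm contrasts.** Assumption: the printed p-values come from paired t-tests (the method column says only t-test). The metabolomic n is not stated. Pairs tried, placebo/probiotics: 7/18, 7/9, 13/18, 7/17, 13/17 (Table 1 describes 13 and 18). Change = second mean minus first; SE = |change| / t quantile at the printed p with n-1 df; the two changes are then compared by a Welch test.

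Clinical_LDL_C at 7/18:
- Probiotics: +0.146, p = 10^-0.548 = 0.283, t = 1.108, SE = 0.132.
- Placebo: -0.187, p = 10^-0.605 = 0.248, t = 1.278, SE = 0.146.
- Difference: 0.146 + 0.187 = +0.333; SE = sqrt(0.132² + 0.146²) = 0.197; t = 1.69; p = 0.11; 95% CI -0.08 to +0.75.

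VLDL_TG at 7/18:
- Probiotics: -0.239, p = 10^-1.355 = 0.044, t = 2.174, SE = 0.110.
- Placebo: -0.006, p = 10^-0.018 = 0.959, t = 0.053, SE = 0.113.
- Difference: -0.233; SE = 0.158; t = -1.48; p = 0.16; 95% CI -0.57 to +0.10.

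The same steps give (range of p over the five pairs of n, unadjusted):

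| Row | Difference in change | p |
|---|---|---|
| Clinical_LDL_C | +0.333 mmol/L | 0.109–0.112 |
| LDL_C | +0.207 mmol/L | 0.109–0.111 |
| VLDL_TG | -0.233 mmol/L | 0.147–0.158 |
| L, XL, XXL VLDL_TG | -0.051, -0.043, -0.055 mmol/L | 0.078–0.089, 0.061–0.069, 0.129–0.142 |
| L, XL, XXL VLDL_L | -0.081, -0.062, -0.085 mmol/L | 0.140–0.151, 0.087–0.095, 0.167–0.179 |
| HDL_TG | -0.021 mmol/L | 0.290–0.294 |
| M, S HDL_C_pct | +2.24, +1.88 points | 0.027–0.036, 0.011–0.013 |
| M, S HDL_CE_pct | +2.28, +2.00 points | 0.025–0.032, 0.010–0.011 |
| M, S HDL_TG_pct | -1.31, -0.88 points | 0.047–0.053, 0.026–0.029 |
| S_LDL_C_pct | +1.32 points | 0.018–0.023 |

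Rounding matters where a change is tiny. The placebo VLDL_TG change of -0.006 could be -0.005 to -0.007, which moves the contrast's t between about -1.3 and -1.6.

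**The case against.** The best defence is that the legend reports rows passing a nominal threshold and that no LDL amount row passes it. The selection is disclosed, LDL-C is reported in Table 2 and Figure 3 (no significant difference), and the legend makes no overall claim that the lipid profile improved. The figure is not visible here and may already plot LDL. The HDL cholesterol and cholesteryl ester percentages, which the legend states first, hold up between arms better than the LDL amounts do. All of this stands, and it rules out any suggestion that LDL was hidden.

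It does not settle the matter. The threshold was applied to within-arm tests. It was not applied evenly: S_LDL_C_pct has p = 10^-2.566 = 0.0027, the third smallest in Table 5 and smaller than any VLDL row, and it is the kind of ratio reported for HDL. Other flagged rows, such as particle sizes and lactate, also go unmentioned, so this omission alone does not show that LDL was singled out. The HDL triglyceride sentence is worded as an amount, but only percentages are flagged.

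A reader might infer that the probiotic raised LDL. The documents do not support that:
- The 25 rows are overlapping measures of the same particles, not 25 results.
- Under the printed headings the direction reverses.
- The contrast's interval includes zero. Free cholesterol in LDL comes closer (difference +0.067 mmol/L, p about 0.06 by the same method), but it is one unadjusted row among about 250.
- S_LDL_C_pct is a composition ratio, and nothing in the documents makes its rise unfavourable.
- Table 2 prints P = 0.0946 for LDL-C change. Its own means and SEMs give a difference of 18.05 mg/dL, SE 7.68, and a Welch p of about 0.03. A rank test, which the methods also allow, might explain the gap. Until that is resolved, neither figure should carry an LDL claim.

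**Conclusion.** The point holds in limited form. The Figure 5 text omits one of the three carriers it names and calls within-arm changes significant. Relative to placebo, clinical LDL-C (+0.33 mmol/L, p about 0.11) and VLDL triglycerides (-0.23 mmol/L, p about 0.15 to 0.16) moved in opposite directions with similar uncertainty, and neither difference is established. None of the VLDL lipid, VLDL triglyceride or HDL triglyceride amounts tabulated above reaches 0.05 between arms. The HDL composition changes are the best supported (cholesterol and cholesteryl ester percentages p about 0.01 to 0.04) but are unadjusted and exploratory.

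The opposite movement of VLDL triglycerides and LDL cholesterol holds under either reading of the columns, because reversing them flips both signs. Which one rose depends on the FC reading. The contrasts rest on paired tests, an assumed n of 7 to 13 on placebo and 9 to 18 on probiotics, and means rounded to three decimals. The LDL_C and VLDL_TG conclusions do not change across those values of n.

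**What to change.** 1. Confirm which column is before and which is after, and correct the headings of Tables 4 and 5 or the FC column.
2. Report the probiotic-minus-placebo difference in change, with 95% CI, adjusted p and the n used, for: Clinical_LDL_C; LDL_C; VLDL triglycerides and VLDL lipids (total and by size); HDL_TG; and the cholesterol-to-lipid and cholesteryl-ester-to-lipid ratios for HDL and LDL alike.
3. Unless that analysis shows otherwise, rewrite the legend to say: no difference from placebo in VLDL, LDL or HDL triglyceride or cholesterol amounts is established; VLDL triglycerides and LDL cholesterol moved in opposite directions relative to placebo; the HDL composition changes are nominal and exploratory. Word the HDL triglyceride finding as a percentage of HDL lipid, which is what the flagged rows measure. Do not state that the probiotic raised LDL.

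The cost is a short re-analysis of data already in hand and a less favourable lipid statement. No new measurements are needed.
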